6.5.5.3. ACR Category used in Stratification (ACR_STRAT)

The ACR category used for stratification (ACR_STRAT) is determined by the randomization list with the following categories:

- ACR \leq 300 mg/g
- ACR >300 mg/g

6.5.6. Electrocardiogram Fridericia Corrected QT Interval

Electrocardiogram intervals are assessed locally at each site.

The following formula is used to calculate the Fridericia corrected QT interval (QTcF) for analysis from QT and RR intervals:

- $QTcF = QT / \sqrt[3]{RR}$ where $RR=60/(\text{Heart Rate})$

6.5.7. ACR adjusted for eGFR

To evaluate ACR after adjusting for filtration rate, $\ln(\text{ACR})/\text{eGFR}$ (Sections 6.5.5 and Section 6.5.4) is assessed.

6.6. Handling of Missing Data

6.6.1. Missing Efficacy Endpoint Data

Missing data will not be imputed for analyses of efficacy endpoints.

6.6.2. Missing Start and Stop Dates for Concomitant Medications

Missing start dates for concomitant medications are not imputed.

Concomitant medications with incomplete end dates are considered concomitant medications if:

- Day and month are missing, and the year is equal to or after the year of the first date of study drug administration;
- Day is missing and the year is after the year of the first date of study drug administration;
- Day is missing and the year is equal to the year of the first date of study drug administration and the month is equal to or after the month of the first date of study drug administration; or
- Year is missing.

6.6.3. Missing Start and Stop Dates for Adverse Events

Treatment-emergent adverse events (TEAEs) are defined in Section 9.1.

Adverse events with incomplete start dates are considered after the date of first dose, if:

- Day and month are missing and the year is equal to or after the year of the first date of study drug dosing;

- Day is missing and the year is after the year of the first date of study drug dosing;
- Day is missing and the year is equal to the year of the first date of study drug dosing and the month is equal to or after the month of the first date of study drug dosing; or
- Year is missing.

Adverse events with incomplete start dates or end dates are considered on or within 30 days of last dose, if:

- Day, month, and year are missing;
- Day and month are missing and the year is equal to or before the year of the date of last dose of study drug plus 30 days;
- Day is missing and the year is equal to or before the year of the date of last dose of study drug plus 30 days and month is equal to or before the month of the date of last dose of study drug plus 30 days.

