## **11.6. Recording Adverse Events**

All conditions present prior to the administration of the first dose of study drug (Day 1) should be documented as medical history. After the first dose, documentation of AEs shall continue until the Week 112 (B) study visit, as indicated in Table 4, regardless of their relationship to study drug or their clinical significance. For patients who discontinue study drug early (prior to Week 100) and continue to be followed in the study, all AEs should be recorded for 12 weeks following the patient's last dose of study drug. Beyond 12 weeks after the patient's last dose, only those AEs that are relevant to the clinical condition including kidney disease, may have an impact on kidney function, or may impact the interpretation of safety or efficacy data must be reported.

AEs that are related to study procedures should be reported independent of the patient's study drug status or duration since the patient's last dose of study drug.

Information to be collected includes type of event, date of onset, date of resolution, investigator-specified assessment of severity and relationship to study drug, seriousness, as well as any action taken.

For guidance on how to handle AEs that change in severity (e.g., worsening or improving), see the eCRF Completion Guidelines. All drug-related (possibly, probably, or definitely related, see Section 11.4) AEs and clinically significant abnormal laboratory test results reported or observed during the study must be followed to resolution (either return to baseline, within normal limits, or stabilization). All non-drug related AEs or clinically significant abnormal laboratory test results will be followed through the Week 112 (B) study visit or for 12 weeks following the last dose for patients who discontinue study drug early.

AEs resulting from concurrent illnesses, reactions to concurrent illnesses, reactions to concurrent medications, or progression of disease states must also be reported. Preexisting conditions (present before the start of the AE collection period) are considered concurrent medical conditions and should NOT be recorded as AEs. However, if the patient experiences a worsening or complication of such a concurrent condition, the worsening or complication should be recorded as an AE. Investigators should ensure that the AE term recorded captures the change in the condition (e.g., “worsening of...”). Any improvement in condition should be documented per Section 9.10.11.

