9.1. Adverse Event Preferred Term and Body/Organ System Summary Tables

Treatment-emergent adverse events are summarized by treatment as defined by the safety analysis set. In addition to being summarized by treatment year, AEs are also summarized overall.

Treatment-emergent adverse events are events that either:

- Have a complete date of onset on or after the date of first dose and not more than 30 days after the date of the last dose of study drug, or
- Have no recorded date of onset with a stop date after the first dose of study drug, or
- Have no recorded date of onset and stop date.

General considerations for TEAE summaries are:

- Multiple events by PT and SOC are counted once only per patient for summaries of TEAE incidence.
- For summaries of TEAE incidence by severity, only the most severe event is counted per patient.
- For summaries of TEAE incidence by relationship, only the most strongly related event is counted per patient.
- A TEAE with a missing resolution date or incomplete date that is not identified as continuing is assumed to be continuing.
- For summaries of the number of TEAEs, all TEAEs are counted.

Off-treatment AEs (OTAEs) are events with a start date more than 30 days after last dose and not considered treatment emergent. Off-treatment AEs will be summarized separately.

Adverse Events are coded using MedDRA. In MedDRA, each verbatim term is mapped to a preferred term and high-level term (HLT), which is then mapped to a SOC.

The investigator grades the severity of the AEs as mild, moderate, or severe as defined in the study protocol. The investigator grades association or relatedness to the study medication according to criteria specified in Section 11.4 of the protocol.

As defined in the protocol, an SAE is an adverse event (occurring at any dose and regardless of causality) that:

- Results in death;
- Is life-threatening;
- Requires inpatient hospitalization or prolongation of existing hospitalization;
- Results in persistent or significant incapacity or substantial disruption of the ability to conduct normal life functions;
- Is a congenital anomaly or birth defect in an offspring of a patient taking study drug;
- Is an important medical event.

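### SAP 6.6.3 lets a missing or year-only end date place an adverse event with a partial but clearly late onset within 30 days of last dose, and for complete onsets it conflicts with 9.1

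*SAP*

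**What the plan says.** SAP 6.6.3 has two lists for incomplete adverse event dates. The first decides whether an event falls after first dose and is limited to incomplete start dates. The second decides whether it falls within 30 days of last dose and is wider: "Adverse events with incomplete start dates or end dates are considered on or within 30 days of last dose, if". Its first condition reads "Day, month, and year are missing". Its second accepts a date with only a year, if that year is not after the year of last dose plus 30 days. Its third compares year and month when only the day is unknown. None of the three says which of the two dates it tests.

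6.6.3 opens by saying "Treatment-emergent adverse events (TEAEs) are defined in Section 9.1". Section 9.1 gives three routes to treatment-emergent (TEAE) status:

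- a full onset date in the window ("Have a complete date of onset on or after the date of first dose and not more than 30 days after" the last dose);
- no onset but a stop date ("Have no recorded date of onset with a stop date after the first dose of study drug, or" the third route);
- neither date recorded.

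It then defines the complement: "Off-treatment AEs (OTAEs) are events with a start date more than 30 days after last dose and not considered treatment emergent". Section 9.1.1 cites 6.6.3 as the place for partial onset dates.

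**The concern.** Treatment emergence is a question of when an event began. The end date bears on it only as an upper bound: an event that had ended by a given day must have begun by then. A missing end date gives no such bound, and a year-only end date gives a weak one. Yet 6.6.3 accepts either as enough to place the event near last dose.

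Late events without an end date are foreseeable. Protocol 11.6 follows non-drug-related events to Week 112 (B) "or for 12 weeks following the last dose for patients who discontinue study drug early". After those 12 weeks an early stopper's events must still be reported if they are relevant to the clinical condition including kidney disease, may affect kidney function, or may affect interpretation of the data. They need not be followed to resolution.

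Any event wrongly placed within 30 days goes into the TEAE tables of SAP 9.1.2 and out of the off-treatment summary. Safety and tolerability are a primary objective in both documents.

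**Working it through.** No figure is stated on this point, so the check applies the rules to test events. The dates are assumed, for illustration only: first dose 2 March 2020, last dose 31 January 2022, so last dose plus 30 days is 2 March 2022 (the cut-off).

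Rule as written (either incomplete date may qualify): a date qualifies if it is (a) wholly missing; (b) year only, with year ≤ 2022; or (c) day missing, with year ≤ 2022 and month ≤ 3.

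| Row | Onset | End | 9.1 | 6.6.3, either date | 6.6.3, start date only |
|---|---|---|---|---|---|
| 1 | 19 Aug 2022 (day 200 after last dose) | missing | off-treatment | within | not applicable |
| 2 | 19 Aug 2022 | 2022 | off-treatment | within | not applicable |
| 3 | 19 Aug 2022 | Sep 2022 | off-treatment | not within | not applicable |
| 4 | Aug 2022 | missing | no criterion | within | not within |
| 5 | 2023 | missing | no criterion | within | not within |
| 6 | Aug 2022 | 2022 | no criterion | within | not within |
| 7 | Aug 2022 | 1 Sep 2022 | no criterion | not within | not within |
| 8 | none | none | TEAE | within | within |
| 9 | 10 Feb 2022 (day 10 after last dose) | missing | TEAE | within | not applicable |
| 10 | Nov 2021 | Jan 2022 | no criterion | within | not within |
| 11 | Nov 2021 | missing | no criterion | within | not within |

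**Complete onset (rows 1 to 3 and 9).** Rows 1 and 2 conflict: 6.6.3 says within 30 days, while 9.1 says off-treatment because the onset meets none of its three routes. Rows 3 and 9 do not conflict.

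**Partial late onset (rows 4 to 7).** In row 4 the start date fails (c), since month 8 > 3, but the missing end date meets (a). The first list of 6.6.3 is also met, because 2022 is after the year of first dose, 2020. The event is therefore placed after first dose and within 30 days of last dose, although August 2022 lies wholly after 2 March 2022. Row 5 is the same with a year-only onset (2023 > 2022). In row 6 the end date meets (b), since 2022 ≤ 2022, although the onset month is already past the cut-off. A complete end date does not trigger the error (row 7).

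**Partial onset while on drug (rows 10 and 11).** These show why the end-date words cannot simply be struck out. November 2021 precedes the cut-off, but condition (c) compares months separately and 11 > 3, so the start date fails. In row 10 the end date January 2022 (month 1 ≤ 3) rightly brings the event in, because an event that ended in January 2022 began by then. In row 11 the missing end date reaches the right answer for the wrong reason.

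**The case against.** The best defence is that 9.1 is the definition and 6.6.3 says so. A complete onset more than 30 days after last dose meets none of the three routes and fits the off-treatment definition. 9.1.1 gives 6.6.3 a narrow job, partial onset dates, so a complete onset is outside it. 9.1 also handles a missing resolution date separately, as a continuing event, with no effect on onset. This stands for complete onsets.

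A reader might go further and infer that late events with a known onset, still unresolved at last contact, are moved into the TEAE tables. The proviso at the end of the off-treatment definition invites this, because it yields to anything that makes an event treatment-emergent, and the SAP states no precedence between its own sections. The documents do not support it. 6.6.3 supplies date conventions and nowhere declares an event treatment-emergent.

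The defence does not reach partial onsets. The first route needs a complete onset and the other two need none, so an onset of August 2022 falls between them and 6.6.3 decides. A sensible programmer might test the start date first, but nothing in the text says to.

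Three points limit the consequence. Drug-related events are to be followed to resolution, and serious events until resolved, chronic or stable (Protocol 11.6 and 11.2.1.2). Safety summaries are descriptive and all adverse events are listed (SAP 9 and 9.1.2). And 9.1 separates events flagged as continuing from those with a missing resolution date; if flagged events are not treated as having an incomplete end date, the affected group is smaller still.

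**Conclusion.** The 30-day rule in 6.6.3 is wrong as written for one group: events with a partial onset whose recorded month or year is clearly after last dose plus 30 days, and an end date that is wholly missing, or year-only and not after the year of that cut-off. These are counted as within 30 days when their own onset says otherwise. For them the error runs one way, into the TEAE tables. For complete onsets there is a contradiction between 6.6.3 and 9.1 to be reconciled, with 9.1 governing.

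The size cannot be computed: the documents give no count of partial onset dates or missing end dates, and no expected rate of early stopping by arm. It is probably small, because it needs two incomplete dates on the same late event. A reader might infer a measurable imbalance between arms from unequal early stopping; no figure in the documents supports one. The conclusion assumes that 6.6.3 is applied literally, with either incomplete date sufficient.

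**What to change.** Amend 6.6.3 to state:

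1. An adverse event with a complete start date is classified by that date alone under 9.1.
2. For an incomplete start date, the 30-day rule is applied to the parts of the start date that are recorded. A missing or incomplete end date never overrides a recorded start month or year later than last dose plus 30 days.
3. An end date may be used only to show that the event ended before first dose, or that it ended on or before last dose plus 30 days and so must have begun by then.
4. Events with neither date remain TEAEs under the third route of 9.1, which keeps the conservative handling of unknown onset.

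Do not simply delete the reference to end dates; row 10 would then lose a genuine TEAE. The way the last condition compares months is a separate matter, but it should be settled in the same edit, with year and month read together as one calendar month. Otherwise step 2 would drop row 11.

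The cost is a few words of SAP text and a line or two of derivation code. No data collection changes.

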9.1.1. Missing and Partial Adverse Event Onset Dates

Rules for handling partial AE Onset Dates are included in Section 6.6.3.

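### SAP 6.6.3 tests year and month separately, so an adverse event with a missing day can fail the last-dose rule although the patient was on drug

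*SAP*

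**What the plan says.** Section 6.6.3 of the SAP has two sets of rules for adverse events with incomplete dates. One decides whether the event came after first dose, the other whether it came on or within 30 days of last dose.

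The last-dose set opens: "Adverse events with incomplete start dates or end dates are considered on or within 30 days of last dose, if". Its final bullet handles dates with only the day missing. It asks for a year equal to or earlier than that of last dose plus 30 days, and joins to this, with a plain conjunction, the requirement that the "month is equal to or before the month of the date of last dose of study drug plus 30 days".

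The first-dose set is built differently. One bullet settles the matter by year alone: "Day is missing and the year is after the year of the first date of study drug dosing". A separate bullet brings in the month only when the years are equal. Section 6.6.2, on concomitant medications, has the same split, and its month comparison begins "Day is missing and the year is equal to the year of the first date of study drug administration".

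Section 9.1 defines a treatment-emergent event through a complete onset date ("Have a complete date of onset on or after the date of first dose and not more than 30 days after" the last dose) or through the absence of any recorded onset date (for example, "Have no recorded date of onset with a stop date after the first dose of study drug"). Off-treatment events are "events with a start date more than 30 days after last dose and not considered treatment emergent". Section 9.1.1 adds: "Rules for handling partial AE Onset Dates are included in Section 6.6.3".

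**The concern.** Year and month together make one point in time. Testing each part separately gives the wrong answer whenever the event year is earlier than the cut-off year but the event's calendar month is later than the cut-off month. Planned treatment lasts 100 weeks, so every completer crosses at least one year boundary and the situation is ordinary.

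A partial onset date is neither complete nor unrecorded, so the definitions in 9.1 do not reach it and 9.1.1 returns it to 6.6.3. If the last bullet fails, 6.6.3 gives no default. Whether an on-drug event counts as treatment-emergent would then depend on the calendar month of the patient's last dose, which has no bearing on exposure. Safety and tolerability is part of the primary objective, and the tables in 9.1.2 by seriousness, severity, relatedness and discontinuation all take their events from this classification.

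**Working it through.** The plan states no figure here, so there is none to reproduce. The check is of the logic, followed by a count of calendar days.

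**Inputs.** The two forms of the rule come from SAP 6.6.3. Treatment length is 100 weeks, or 700 days (protocol and SAP study design). SAP Section 2 gives 10 May 2023 as the study drug termination date; I use it as an example last-dose date, which is an assumption. The other last-dose dates below are also assumed.

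**Rules compared.** Let C be last dose plus 30 days, and let y and m be the event year and month.

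- As written: y ≤ year(C) and m ≤ month(C).
- Chronological: y < year(C), or y = year(C) and m ≤ month(C).

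**One event.** Last dose 10 May 2023 gives C = 9 June 2023. For an onset in November 2021, the year test passes (2021 ≤ 2023) and the month test fails (11 > 6), so the rule as written rejects it. The chronological rule accepts it because 2021 < 2023. A patient on drug for 700 days to that date started on 10 June 2021 and was on treatment throughout November 2021.

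**Share of on-drug days in failing months.** July to December has 31 + 31 + 30 + 31 + 30 + 31 = 184 days.

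| Last dose | C | Days on drug | Failing days | Share |
|---|---|---|---|---|
| 10 May 2023 | 9 Jun 2023 | 700 | 184 + 184 = 368 | 52.6% |
| 10 May 2023 | 9 Jun 2023 | 364 | 184 | 50.5% |
| 10 May 2023 | 9 Jun 2023 | 84 | 0 | 0% |
| 1 Jan 2022 | 31 Jan 2022 | 700 | 700 − 32 = 668 | 95.4% |
| 15 Nov 2022 | 15 Dec 2022 | 700 | 0 | 0% |

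In the fourth row only January days pass: 31 in January 2021 and 1 in January 2022. In the last row the cut-off month is December, so no month can exceed it. In the 84-day row, treatment lies wholly within 2023 and before June.

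**Direction of the month test on the start date.** If y ≤ year(C) and m ≤ month(C), then (y, m) is never later than the year and month of C. The rule as written therefore never accepts a start date that the chronological rule would reject. Its errors on the start date are all rejections.

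**The case against.** The best defence is that this is a drafting slip which a programmer would recognise from the correctly branched rules beside it, and that the sentence could be read as one combined year-month comparison. That reading is possible, but the text does not say it, and the explicit branching in the neighbouring rules argues against it.

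A second defence stands in part. The last-dose rule refers to start dates or end dates. If either may satisfy it, some events that fail on the start date are accepted through an incomplete end date. A wholly missing end date could meet the first bullet, and an end date giving only the year could meet the second. By the same route a late event with a partial start and no end date could also be accepted. A reader might infer that the section as a whole can only undercount treatment-emergent events. That holds for the month test on the start date, not for the section.

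A reader might also infer that rejected events move to the off-treatment table. The documents do not support this: the off-treatment definition requires a start more than 30 days after last dose, which an on-drug onset does not meet. The event is left without a class.

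Nor do the day shares mean that about half of treatment-emergent events would be lost. They are shares of calendar days, not of events, and any average depends on assumed start dates and onset timing. With 209 weekly first doses from 1 May 2019 to 26 April 2023 and treatment cut off at 10 May 2023, the mean share is 42% if onset is uniform over treatment and 59% if onset is confined to the first 56 days.

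Finally, the events remain visible. Section 9.1.2 lists all adverse events, deaths, serious events and those leading to permanent discontinuation, and the safety analysis is descriptive unless otherwise specified.

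**Conclusion.** The last bullet of SAP 6.6.3 is wrong as written. An adverse event with the day missing and the month and year present fails the last-dose rule on its start date if its year is earlier and its calendar month later than those of last dose plus 30 days, even though the patient was on drug. No other provision classifies it.

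The scope is narrow. Events with complete dates, with only the year recorded, or with no date at all are not touched by the month test. For 100 weeks of treatment, the share of on-drug days in failing months runs from 0% (December cut-off) to about 95% (January cut-off). Here on drug means between first and last dose, ignoring interruptions and the Week 48–52 gap before protocol version 6. The documents do not say how many events lack only the day, so the effect on the tables is unknown and could be nil. No efficacy result or analysis population depends on it. It should be corrected because a stated rule gives a wrong result and the remedy is simple.

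A separate, minor mismatch: Section 9.2 removes only Weeks 100–104 from the compliance denominator, while follow-up runs to Week 112 and the 80% count is stated through Week 100. If participation is counted to Week 112, a fully adherent completer scores 700 / (784 − 28) = 92.6%. A reader might infer that the 80% count is distorted. This example does not show that, since the patient stays above the threshold, and the summary is descriptive only.

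**What to change.** Replace the last bullet of 6.6.3 with two branches. A day-missing date qualifies if its year is earlier than the year of last dose plus 30 days. It also qualifies if the years are equal and its month is no later than the month of last dose plus 30 days. Add a sentence stating that the start date governs treatment-emergent status whenever any part of it is recorded. This closes the end-date route in both directions.

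Separately, end the compliance denominator in 9.2 at Week 100, less the Week 48–52 gap where it applies, so that the formula matches the reported scope.

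The cost is one bullet and one sentence in 6.6.3, one sentence in 9.2, and small programming edits. No new data are needed.
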